7.3.2 Key Secondary endpoint analyses

The analysis for the key secondary endpoint, for patients achieving a GPPGA score 0 or 1 at Week 1, will be performed in the same manner as described for the analyses of the primary endpoint.

Any use of escape medication, e.g. use of restricted medication for disease worsening in [Table 4.2.2.1: 1](#), prior to observing the key secondary endpoint is considered to reflect a failure to achieve the endpoint outcome, i.e. non-response (see key secondary endpoint definition [Section 2.1.3](#)).

7.3.3 Secondary endpoint analyses

The treatment effect on the following secondary endpoints, 1) the proportion of patients achieving a GPPASI 75 at Week 4, 2) the change from baseline in pain VAS at week 4, 3) the change from baseline in total PSS score at week 4, and 4) the change from baseline in the total FACIT-Fatigue score at Week 4, will be tested in a hierarchical manner as a part of the pre-specified testing strategy, subsequent to the test of the primary endpoint and key secondary endpoint, which is defined in [Section 7.2](#).

The analysis for the proportion of patients achieving a GPPASI 75 at Week 4 (where any use of escape medication/OL BI 655130 at D8/rescue treatment with BI 655130 prior to observing the endpoint(s) is considered to represent a failure to achieve the endpoint outcome, i.e. non-response) will be performed using the same approach as that defined for the primary endpoint analysis of the study based on the RS.

For the analysis of the continuous secondary endpoints which are included in the statistical testing strategy, the following estimand and testing approach will be implemented:

Any use of escape medication or OL BI 655130 at Day 8 or rescue medication with BI 655130 prior to an assessment timepoint will be considered as a non-response at this timepoint and assigned worst treatment outcomes in the analysis.

The effect of BI 655130 vs placebo will be evaluated by a Wilcoxon rank test using the randomized set. Any assessments after the use of escape medication or OL BI 655130 at D8 or rescue medication with BI 655130 will be assigned worst case ranks for the testing. Missing data will be further imputed and handled via assignment of ranks. All details regarding the ranking rules for test are defined in [Table 7.5:1](#).

Sensitivity analysis for secondary endpoints will be described in TSAP.

[figure not shown]
Other secondary endpoints

For all patients who were treated with BI 655130 either through initial randomization, or through OL BI 655130 at D8, additional summaries of the following endpoints at Week 4 will be done where any use of escape medication prior to Week 4 is considered to represent a non-response:

- The proportion of patients with GPPGA 0 or 1 at Week 4,
- The proportion of patients with a GPPGA pustulation subscore of 0 indicating no visible pustules at Week 4

Other secondary endpoints will be presented in an exploratory manner using the methods described above. Frequencies and percentages will be presented for categorical endpoints; descriptive statistics will be used for continuous data. If applicable, 95% confidence intervals will also be displayed.

Analysis of treatment emergent AE will be described in [Section 7.3.5](#).

7.3.5 Safety analyses

Adverse events will be coded using the current version of Medical Dictionary for Regulatory Activities (MedDRA) coding dictionary. Standard BI summary tables and listings will be produced.

All treated patients will be included in the safety analysis. In general, safety analyses will be descriptive in nature and will be based on BI standards. No hypothesis testing is planned. Statistical analysis and reporting of adverse events will concentrate on treatment-emergent adverse events. To this end, all adverse events occurring between start of treatment and end of the residual effect period will be considered 'treatment-emergent'; the residual effect period (REP) is defined as 16 weeks after the last dose of trial medication. Note that for patients who continue into the extension trial, TEAE up to the first dose in the extension trial will be available for display in the current study. Adverse events that start before first drug intake and deteriorate under treatment will also be considered as 'treatment-emergent'. For all subjects who received OL BI 655130 at D8 or rescue medication with BI 655130, safety assessments including adverse events, laboratories, vital signs etc. which occurred subsequent to such intake will be excluded from presentations according to the planned treatments; these data will, however, be included in summaries where all data after any use of BI 655130 are displayed.

Frequency, severity, and causal relationship of adverse events will be tabulated by system organ class (SOC) and preferred term after coding according to the current version of the MedDRA.

The exposure adjusted incidence rate (per 100 subject years) of a selected treatment emergent adverse event is defined as the number of subjects experiencing the adverse event per treatment group during time at risk divided by the total time of subjects at risk in that treatment group to contribute the event to the analysis multiplied by 100 (per 100 subject years), where:

[figure not shown]
$$\text{Time at risk [subject years]} = (\text{date of onset of TEAE} - \text{study drug start date} + 1) / 365.25$$

[figure not shown]
If, for a subject, the selected treatment emergent adverse event didn't occur then the time at risk will be censored at min (date of death, last contact date per EoS page for patients who will not be rolled over to OLE study, the first dose of OLE study for patients who will be rolled over to OLE study, drug stop date + 112 days, date of Day 8 if OL BI 655130 is given, date of rescue medication if BI 655130 is given). For each selected treatment emergent AE, the exposure adjusted incidence rate will be calculated as:

Incidence rate [1/100 Subject years (pt-yrs)] = 100 * number of subjects with AE /
Total AE-specific time at risk [subject years].

Laboratory data will be analyzed both quantitatively as well as qualitatively. The latter will be done via comparison of laboratory data to their reference ranges. Values outside the reference range as well as values defined as clinically relevant will be highlighted in the listings. Treatment groups will be compared descriptively with regard to distribution parameters as well as with regard to frequency and percentage of patients with abnormal values or clinically relevant abnormal values.

Vital signs, physical examinations, or other safety-relevant data observed at screening, baseline, during the course of the trial and at the end-of-trial evaluation will be assessed with regard to possible changes compared to findings before start of treatment.

7.4 INTERIM ANALYSES

No interim analysis is planned in this trial.

In order to ensure the patient's safety during the trial, a fully external DMC, independent of the trial and project teams, will review all available unblinded safety data as well as selected efficacy data at regular intervals following first-patient-in. A DMC SAP which describes the analyses required for assessment by the DMC will be produced. Further details will be provided in a DMC charter.

7.5 HANDLING OF MISSING DATA

Every effort will be made to collect complete data at all visits. However, missing data will still occur and approaches to handle this are proposed below.

For primary and key secondary and secondary binary endpoints

With regards to the handling of missing data on the primary, key secondary and secondary binary efficacy endpoints, a Non Response Imputation will be applied as the primary imputation approach that is, imputing as a failure to achieve a response, however:

- If there are available data at the visits both before and after the visit with a missing outcome, then impute as a success only if both the preceding and the following

Proprietary confidential information © 2020 Boehringer Ingelheim International GmbH or one or more of its affiliated companies

observations also represent a success and there is no use of escape medication, OL BI 655130 at D8 or rescue medication with BI 655130 within this imputation period;

- Otherwise, impute as a failure to achieve a response (i.e. no response imputation [NRI]).

NRI is a conservative imputation scheme because it assumes that withdrawal (or missing data due to any other reason) is related to treatment failure. Other imputation schemes will therefore be considered for the primary, key secondary and secondary binary efficacy analyses including:

- Best response imputation: impute all missing values based on the best response observed at visits prior to withdrawal/occurrence of missing data. If there is no non-missing data available, then the missing value will be imputed as a failure.
- If fewer than 3 patients have missing data on an endpoint at Week 1 then a list of all possible treatment differences will be generated whereby each of the potential responses (response, non-response) will be imputed for each patient in an exhaustive manner.

For secondary continuous endpoints

For secondary continuous endpoints at Week 4 which are included into the statistical testing strategy, the Wilcoxon rank test will be used.

In test, worst case ranks will be assigned to those with prior escape medication or OL BI 655130 at D8 or rescue medication with BI 655130 or death, and for patients with missing data at Week 4 for other reasons, LOCF method will be used for imputation.

The best possible baseline values are the lowest value 0 for Pain VAS and PSS and the highest value 52 for FACIT-Fatigue scale. The worst possible post-baseline values are the highest values 100 and 16 for Pain VAS and PSS and the lowest value 0 for FACIT-Fatigue scale. Therefore, the maximum value for the worst possible change from baseline (i.e., the worst possible post-baseline value - best possible baseline value) is 100 for Pain VAS, 16 for PSS and -52 for FACIT-Fatigue scale.

The ranking rules are outlined in [Table 7.5:1](#).

Table 7.5: 1

Ranking rules for secondary continuous endpoint

	Category	Ranking	Case description	Imputed change from baseline for further ranking score*
1	Missing data at week 4 but still alive and no use of either escape medication, OL BI 655130 at D8 or rescue medication with BI 655130 prior to Week 4.	Ranked by imputed value	Patient has available data at visit prior to Week 4	LOCF prior to Week 4
			Patient has no post-baseline value	102 for Pain VAS 18 for PSS and -54 for FACIT-Fatigue scale
2	Use of escape medication, OL BI 655130 at D8 or rescue medication with BI 655130 prior to Week 4 but still alive.	Ranked by OL BI 655130 at D8 or time to rescue medication or time to escape medication from randomization;	Patient has OL BI 655130 at D8 and has no escape medication or rescue medication prior to Week 4;	104 for Pain VAS 20 for PSS and -56 for FACIT-Fatigue scale

Table 7.5: 1

Ranking rules for secondary continuous endpoint (cont'd.)

	Category	Ranking	Case description	Imputed change from baseline for further ranking score*
			Patient has rescue medication with BI 655130 x days from randomization and has no escape medication prior to Week 4;	106-x/1000 for Pain VAS 22-x/1000 for PSS and -58+x/1000 for FACIT-Fatigue scale
			Patient has escape medication y days after randomization and prior to Week 4;	108-y/1000 for Pain VAS 24-y/1000 for PSS and -60+y/1000 for FACIT-Fatigue scale
3	Patient died before the measurement at Week 4	Ranked by time to death from randomization	Patient died z days after randomization	110-z/1000 for Pain VAS 26-z/1000 for PSS and -62+z/1000 for FACIT-Fatigue scale

* Ranked values in this table are only for purpose of rank tests but not for any descriptive displays

With respect to safety evaluations, it is not planned to impute missing values.

7.6 RANDOMISATION

BI will arrange for the randomization and the packaging and labeling of trial medication. The randomization list will be generated using a validated system, which involves a pseudo-random number generator so that the resulting treatment will be both reproducible and non-predictable. Access to the codes will be controlled and documented.

Stratification for Japan versus non-Japan will be done in order to assure that sufficient patients per treatment group are recruited specifically to support individual country submission in Japan; these strata will be treated as operational strata and will not be included into the analyses of efficacy endpoints.

Within each stratum (Japan vs. non-Japan), patients will be randomized in a 2:1 ratio (BI 655130 vs. Placebo). The randomization will be done in blocks to achieve balanced allocation. The block size of the randomization will be documented in the CTR.

The process of randomization is done via an IRT. Practical aspects of the treatment allocation process are detailed in [Section 4.1.3](#).

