7. STATISTICAL METHODS AND DETERMINATION OF SAMPLE SIZE

7.1 STATISTICAL DESIGN – MODEL

This trial is designed as a randomized, parallel-group, double-blind, and placebo-controlled trial with one active dose of BI 655130 in patients with GPP presenting with an acute flare of moderate to severe intensity.

The primary objective of this trial is to evaluate the efficacy, safety and tolerability of a single i.v. dose of BI 655130 in comparison to placebo at Day 1. The primary analysis, on each of the binary, primary endpoint, achievement of a GPPGA pustulation subscore of 0 at Week 1, and key secondary endpoint, achievement of a GPPGA of (0, 1) at Week 1, where any use of escape medication prior to observing the endpoint is considered to be a non-response, will compare the proportion of patients who achieve a response on BI 655130 to Placebo. Given the small sample size proposed to be used in this trial, an exact statistical test, the Suissa-Shuster Z-pooled test, will be used to perform the primary analysis. Confirmation of efficacy is then given if the proportion of patients achieving a response on the primary endpoint is statistically significantly higher for BI 655130 than for placebo. Formal statistical hypothesis testing will be performed at an overall 1-sided alpha level of 0.025.

Stratification of randomization will be performed in this trial for Japan versus non-Japan. This stratification is implemented for operational purposes only and is not intended to be used as an adjustment factor in the primary analyses of efficacy (see [Section 7.6](#)).

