7.3.1 Primary endpoint analyses

The analysis for the primary endpoint includes the evaluation of patients achieving a GPPGA pustulation subscore of 0 at Week 1.

Any use of escape medication, e.g. use of restricted medication for disease worsening in [Table 4.2.2.1: 1](#), prior to observing the primary endpoint is considered to reflect a failure to achieve the endpoint outcome, i.e. non-response (see primary endpoint definition in [Section 2.1.2](#)).

Due to the small sample size of the trial, an exact statistical test will be used to assess the statistical significance of the treatment effect versus Placebo. Since the traditional Fisher's exact test may be unnecessarily conservative, an alternative test, the Suissa-Shuster Z-pooled test, will be implemented in this trial. The Suissa-Shuster Z-pooled test always preserves the type I error level and is usually more powerful than the Fisher's exact test.

The primary endpoint will be tested, for the RS, using the Suissa-Shuster Z-pooled test at a 1-sided, alpha level of 0.025.

Secondary analysis of the primary endpoint will include:

- A sensitivity analysis utilizing the PPS;
- Analysis of an additional estimand whereby any use of escape medication prior to week 1 will be considered to represent a non-response. For patients who use other restricted medication but not for disease worsening prior to Week 1, data will be censored for further analysis following the use and imputed using the methods described in [Section 7.5](#).
- Sensitivity analyses which utilize alternative methods for the handling of missing data as described in Section 7.5.
- A subgroup assessment according to the Japan vs. non-Japan strata will be assessed descriptively
- Sensitivity analyses to adjust for the covariates, IL36R mutation status (Yes vs. No) and baseline GPPGA total score (3 vs. 4) respectively using logistic regression.

Further analysis of the primary endpoint will include:

- Analysis of the time to first achievement of a response on the primary endpoint via Kaplan-Meier methods.

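### Randomisation is stratified by Japan v non-Japan, but no visible efficacy analysis uses the strata: harmless to validity and stated power, but a cheap gain is left unused on the rank tests

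*Protocol*

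**What the plan says.** Protocol 7.6: "Within each stratum (Japan vs. non-Japan), patients will be randomized in a 2:1 ratio", in blocks. The stated purpose is to recruit enough patients per group for a submission in Japan, and "these strata will be treated as operational strata and will not be included into the analyses of efficacy endpoints". Protocol 7.1 agrees: the factor "is not intended to be used as an adjustment factor in the primary analyses of efficacy".

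The analyses follow that line:
- **Binary endpoints.** Protocol 7.3.1: "The primary endpoint will be tested, for the RS, using the Suissa-Shuster Z-pooled test at a 1-sided, alpha level of 0.025". The PROC FREQ code in SAP 7.4 has no stratum term. The key secondary endpoint and GPPASI 75 use the same test.
- **Continuous Week 4 endpoints** (pain VAS, PSS, FACIT-Fatigue). Protocol 7.3.3: "The effect of BI 655130 vs placebo will be evaluated by a Wilcoxon rank test using the randomized set". The NPAR1WAY code in SAP 7.5.2 is unstratified.
- **Sensitivity models.** The logistic models in SAP 7.4 adjust for IL36R mutation status and for baseline GPPGA. The MMRM in SAP 7.5.2 has baseline, visit and treatment. Region is in neither.
- **Region itself** appears only as a descriptive subgroup of the primary endpoint (Protocol 7.3.1).

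SAP 6.4, which defines the subgroups, is not in the public text, so nothing is inferred from it.

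**The concern.** Stratified blocks hold the arms close to 2:1 within each region, so a regional difference in response can hardly unbalance the comparison. An unstratified test still counts that difference as noise. If region predicts outcome, the test's true size falls below its nominal level and it detects less than a test that respects the design.

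The documents give some reason to think region could matter. Protocol 3.2 notes that standards of care differ between countries and that several biologics are registered for GPP only in Japan. Protocol 5.6 says the characteristics of psoriasis may differ by race. The plan also specifies adjusted sensitivity analyses for two factors that were not stratified and none for the one that was.

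Three of the four Week 4 tests in the confirmatory hierarchy are rank tests, and Protocol 7.2 says the study is not further powered for them. Sensitivity that can be had cheaply is worth most there.

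**Working it through.** **Inputs from the documents:** 51 patients, 34:17; one-sided alpha 0.025; expected rates 0.6 v 0.1; endpoint correlation 0.65 (Protocol 7.1, 7.7). **Assumed:** 6 to 18 Japanese patients, exact 2:1 within strata (block size is not given), and the size of the region effect.

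**1. Reproduce the plan's figure.** With x_T and x_C responders and p = (x_T + x_C)/51, the statistic is

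Z = (x_T/34 − x_C/17) / sqrt[ p(1 − p)(1/34 + 1/17) ].

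Maximising the rejection probability over the common null rate gives critical value 2.048 and maximum size 0.0238. Exact power at 0.6 v 0.1 is 96.28% (stated 96.3%). Simulated joint power is 93.8% (stated 93.9%). All eight rows of Table 7.7: 1 reproduce within 0.3 points.

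**2. Size of the planned test when region is prognostic** (average null rate 0.3, 6 to 15 Japanese patients):

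| Region odds ratio | Type I error |
|---|---|
| 1 | 0.0196 |
| 2 to 3 | 0.0168–0.0192 |
| 5 | 0.0138–0.0183 |
| 10 | 0.0090–0.0178 |

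So the test is conservative, increasingly so as the region effect grows. Over all pairs of stratum null rates it never exceeds 0.0238.

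**3. Binary power with overall rates held at 0.6 v 0.1** (6 to 15 Japanese patients, region effect in either direction). The stratified comparator is a Mantel-Haenszel test: responders on active minus their expected number, summed over strata and divided by its standard error. Its exact unconditional critical value is set by maximising size over both stratum rates.

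| Region odds ratio | Planned, unstratified | Exact unconditional, stratified |
|---|---|---|
| 2 to 3 | 96.3–96.6% | 95.5–96.4% |
| 5 | 96.5–96.8% | 96.2–97.1% |
| 10 | 96.6–97.3% | 96.7–98.2% |

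The planned test does not drop below its design power. The stratified test pays only at odds ratios of about 5 or more. The largest gain at 0.6 v 0.1 is about 1 point; at 0.5 v 0.1 it is about 3 points (87.3% v 90.6%, 15 Japanese patients, odds ratio 10). If region is irrelevant, stratifying costs 0.6–0.7 points at 0.6 v 0.1 and 2–3 points at 0.5 v 0.1 (12 or 18 Japanese patients).

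Two simpler stratified tests do worse. At odds ratio 2 to 3 the exact conditional version has 93.9–94.9% power. The asymptotic version reaches 96.9–97.5%, but with maximum size 0.039–0.043, above 0.025.

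**4. Rank tests.** With W the rank sum on active, Wilcoxon uses z = (W − 34·52/2) / sqrt(34·17·52/12). Van Elteren ranks within strata, with n_s patients in stratum s, of whom a_s are on active and b_s on placebo. It uses z = Σ[W_s − a_s(n_s+1)/2]/(n_s+1), divided by sqrt(Σ a_s·b_s/[12(n_s+1)]). Power for an illustrative 0.9 SD effect, normal outcome, 20,000 simulated trials per setting:

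| Japanese patients | Region shift | Wilcoxon | Van Elteren | Difference |
|---|---|---|---|---|
| 6 | 0 | 82.1% | 81.7% | −0.4 |
| 9 | 0 | 81.9% | 81.4% | −0.5 |
| 15 | 0 | 82.1% | 81.4% | −0.7 |
| 6 | 0.5 SD | 81.5% | 81.6% | +0.1 |
| 9 | 0.5 SD | 80.7% | 81.4% | +0.7 |
| 15 | 0.5 SD | 80.5% | 81.4% | +0.9 |
| 6 | 1 SD | 79.2% | 81.5% | +2.3 |
| 9 | 1 SD | 77.5% | 81.3% | +3.8 |
| 15 | 1 SD | 76.2% | 81.9% | +5.7 |

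At a 1 SD shift the Wilcoxon type I error is 0.016–0.019; van Elteren stays at about 0.023–0.025.

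Many patients will actually carry worst ranks because of escape or open-label treatment (SAP Table 6.6.2: 2). A simulation with such ties, 6 to 18 Japanese patients and assumed effects, gives the same pattern:
- no region effect: cost about 0.6 points or less;
- 0.5 SD shift (odds ratio 2 for non-response): gain about 0.5–1 point;
- 1 SD shift (odds ratio 4): gain about 3–9 points, with size at or below 0.025.

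**The case against.** **A disclosed choice.** Protocol 7.1 and 7.6 both exclude the strata and 7.6 gives the reason for stratifying; nothing contradicts them. This stands. It explains why the strata exist, though not why an analysis should ignore them.

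**No validity problem.** Protocol 7.3.1 says "The Suissa-Shuster Z-pooled test always preserves the type I error level", and the check confirms it. This stands.

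**At moderate region effects, stratifying the binary tests does not help.** This stands too, and is why the primary test should not change.

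**The rank-test gain is small unless the region shift is near 1 SD, and those endpoints are not powered.** True, but the premium is under 1 point, and low power argues for the more sensitive test.

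**A stronger reading that does not hold.** A reader might infer that power collapses if region is prognostic. Take rates of 0.85 v 0.4 in Japan and 0.4 v 0.05 elsewhere, with 12 Japanese patients (8:4). The planned test then has 79.2% power, against 96.3% by design. But the overall rates have also changed:
- active: (8 × 0.85 + 26 × 0.4)/34 = 0.506;
- placebo: (4 × 0.4 + 13 × 0.05)/17 = 0.132.

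At those overall rates with no region effect, power is 77.3%. With 0.9 v 0.5 and 0.35 v 0.05 the pair is 64.3% with the region effect and 63.1% without. So the fall comes from a smaller assumed treatment effect. Only the gap to a stratified test belongs to this point (82.5% v 79.2%, and 72.8% v 64.3%), and it needs region odds ratios of 8.5 to 12.7 and 16.7 to 19. A null size near 0.005 likewise needs null rates of 0.7 and 0.1, an odds ratio of 21. The documents support no effect of that size. Protocol 3.2 raises differences in care to explain the lack of an active control and does not say that region predicts Week 1 clearance.

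**Conclusion.** The point holds as a minor one. The stratification factor is left out of every visible efficacy analysis, and this makes the tests conservative if region is strongly prognostic. It does not inflate type I error and does not erode the stated 96.3% and 93.9% at the planned overall rates.

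For the binary endpoints, replacing the test is a trade-off of about a point either way at 0.6 v 0.1, with no case for change unless the region odds ratio is about 5 or more. For the continuous endpoints the balance favours stratifying: under 1 point lost if region is irrelevant, roughly 2 to 9 points gained at a shift near 1 SD, and little either way at 0.5 SD.

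All of this rests on an assumed Japanese share, assumed region effects, an exact 2:1 split within strata and, for the rank tests, an illustrative treatment effect.

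**What to change.** - **Keep** the unstratified Suissa-Shuster Z-pooled test as the primary analysis of the binary endpoints. Sample size, alpha and the hierarchy do not change.
- **Replace** the unstratified Wilcoxon test with the Japan-stratified van Elteren test for pain VAS, PSS and FACIT-Fatigue at Week 4, with the same worst-rank rules. The current code requests an exact p-value, so take this one from re-randomisation within strata.
- **Add**, for the primary, key secondary and GPPASI 75 endpoints, a Japan-stratified exact Mantel-Haenszel test and a stratified risk difference as a sensitivity analysis. It would sit beside the IL36R and baseline GPPGA adjustments already planned for the first two. Use the exact unconditional form, because the asymptotic one can exceed 0.025.
- **State** what happens if a stratum contains only one arm, since it then contributes nothing to a stratified test.

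**Cost.** SAP wording, a short program and a power loss below 1 point on the rank tests if region does not matter. The rank-test change departs from Protocol 7.3.3 and 7.6, so those sections need aligning, or the change needs recording in SAP Section 4, before unblinding.
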